11.2 Medical History

The medical history will be summarized from the “Medical History details” eCRF page, using MedDRA, preferred term as event category and system organ class (SOC) body term as Body System category. Each participant will be counted only once within each PT or SOC.

Listing will also be provided.

12 Previous or Concomitant Medications/Procedures

Previous or concomitant medication will be presented based on FAS analysis set for Cohort A and will be presented by ATC and Preferred Name, per parent study exposed group and total. Listing will also be provided.

Previous and concomitant medications are medications, other than parent study medications (i.e. cladribine or placebo), which are taken by patients any time on-trial before or on or after CLASSIC Study Visit 1.

Handling of missing or partial dates are critical for medications identified as DMD that will determine timing of DMD in responders/non-responders and prior DMD use variables. All missing/incomplete dates will be imputed as described in Section 9.5.

Medications in CLASSIC

Medications in CLASSIC are medications which are taken by subjects at any time after (>) the end of the parent study day. Reporting will be done for Cohort A, FAS analysis set.

Disease modifying drugs in CLASSIC

MS-DMDs drugs will be identified using lookup list against all concomitant medication reported as well as eCRF dedicated question. Coding group will provide initial list using drug code, ATC and other elements for the medical team to review and approve prior to data base lock. Final list will be similar to table 3 below and will be standalone document (Appendix 17.2). First, Second, third and any subsequent DMD after first and last dose of Cladribine will also be reported descriptively. Each one will be identified based on the date of the DMD in ascending order since the date of first dose of IMP. First subsequent DMD will be reported by DMD type and ATC and second and third subsequent DMDs will be reported by DMD type only. First subsequent DMD will also be summarized by type, ATC and Medication Name. Patterns of DMD switches will be described also and provided only for the final analysis. Reporting will be done for all cohort, FAS analysis set.

A listing of subsequent DMDs after last IMP dose will be provided for subjects with repeating DMD types.

Table 4: List of MS-DMD

Drug Name	ATCs	SDGs (Standard Drug Groupings)
Alemtuzumab (Campath, MabCampath, Lemtrada)	L01XC, Monoclonal antibodies L04AA, Selective immunosuppressants	Antineoplastic immunosuppressants Monoclonal antibodies - antineoplastics Selective immunosuppressants
Daclizumab (Zinbryta)	L04AC, Interleukin inhibitors	Interleukin inhibitors Monoclonal antibodies - non antineoplastics
Dimethyl fumarate (Tecfidera)	L04AX, Other immunosuppressants	Other immunosuppressants
Fingolimod (Gilenya)	L04AA, Selective immunosuppressants	Selective immunosuppressants
Glatiramer acetate (Copaxone)	L03AX, Other immunostimulants	Other immunosuppressants
interferon beta (Avonex, Rebif, Betaferon, Extavia, Plegridy)	L03AB, Interferons S01AD, Antivirals	Interferons Other antivirals
Laquinimod (Nerventra)	L04AX, Other immunosuppressants N07XX, Other nervous system drugs	Other immunosuppressants

Drug Name	ATCs	SDGs (Standard Drug Groupings)
Mitoxantrone (Novantrone)	L01DB, Anthracyclines and related substances	Antineoplastic anthracyclines and related substances BCRP inhibitors BCRP substrates
Natalizumab (Tysabri)	L04AA, Selective immunosuppressants	Biologic DMARDs Monoclonal antibodies - non antineoplastics Selective immunosuppressants
Ocrelizumab (Ocrevus)	L04AA, Selective immunosuppressants	Biologic DMARDs Monoclonal antibodies - non antineoplastics Selective immunosuppressants
Rituximab (Rituxan)	L01XC, Monoclonal antibodies	Antineoplastic CD20 antigen inhibitors Biologic DMARDs Monoclonal antibodies - antineoplastics
Siponimod	L04AA, Selective immunosuppressants	Selective immunosuppressants
Teriflunomide (Aubagio)	L04AA, Selective immunosuppressants	BCRP substrates Moderate CYP2C8 inhibitors Non-biologic DMARDs OATP1B1 inhibitors Selective immunosuppressants
Hematopoietic stem cell transplant	B05AX, Other blood products	Other blood products
Off-label immunosuppressants (azathioprine, mycophenolate, cyclophosphamide)	L04AX, Other immunosuppressants - azathioprine L04AA, Selective immunosuppressants - mycophenolate L01AA, Nitrogen mustard analogues - cyclophosphamide	Other immunosuppressants - azathioprine Selective immunosuppressants - mycophenolate Non-biologic DMARDs - cyclophosphamide
FINGOLIMOD HYDROCHLORIDE	L04AA, Selective immunosuppressants	Selective immunosuppressants
FUMARIC ACID	D05AX, Other antipsoriatics for topical use D05BX, Other antipsoriatics for systemic use L04AX, Other immunosuppressants V91, Homeopathic preparation	Other immunosuppressants
INTERFERON BETA-1B Betaferon, Extavia???	L03AB, Interferons	Interferons
MITOXANTRONE HYDROCHLORIDE	L01DB, Anthracyclines and related substances	Antineoplastic anthracyclines and related substances BCRP inhibitors BCRP substrates
PEGINTERFERON BETA-1A	L03AB, Interferons	Interferons

13 Study Treatment: Compliance and Exposure

Not Applicable.

14 Efficacy Analyses

No formal statistical hypothesis will be tested, as the study is designed to be exploratory. All analyses will be performed by parent study treatment group and for cohort A except when otherwise specified. In case of low number of participants within a subgroup category as described in section 8.2.2, the subgroup analysis will not be performed for the corresponding efficacy analysis.

14.1 Primary Endpoint

The primary efficacy endpoint of this study will be evaluated descriptively by percentage and 95% CI of patients using a wheelchair most of the time ($EDSS \geq 7$) in the 3 months prior to Study Visit 1 or patients bedridden any time prior to visit 1. Forest plots will also be used to display these results.

In addition, analysis will be adjusted via logistic regression with parent studies (CLARITY or ORACLE), treatment group, and disease duration (at study visit 1) as continuous variable as factors for cohort A and with only disease duration (at study visit 1) as factors for cohort B, C and D. Estimate with likelihood based 95% CI within each parent study treatment group (exposed/not exposed) will be presented.

To identify the primary endpoint, the following source data used will be:

- Both AWB eCRF page and retro EDSS page will be considered. ($EDSS \geq 7$ in the 3 month prior to SV1 or $EDSS \geq 8$ after FDIMP)
- $EDSS \geq 7$ will also be considered (EDSS SV1).
- Participants who died due to MS are included in this proportion also (reason of death is MS disease related).

Disease duration = $(SV1 - \text{date of MS diagnosis} + 1) / 365.25$

Date of MS diagnosis is taken from CLARITY eCRF for CLARITY and CLARITY EXTENSION patients. For ORACLE MS patient, the MS diagnosis is the date of CDMS conversion collected either during the parent study or after the end of the parent study until SV1.

Logistic Regression:

The following SAS code will be used:

```
proc genmod data=sourcedata;
where avalc ne "U";
class STUDY TRT ;
model avalc = STUDY TRT DISEASE_DUR /dist=binomial link=logit lrci wald;
  Estimate "Never Exposed to Cladribine" intercept 1 Trt 1 0 / exp e;
  Estimate "Exposed to Cladribine" intercept 1 Trt 0 1 / exp e;
  Estimate "Never Exposed to Cladribine vs Exposed to Cladribine" Trt -1 1
/exp e;
  lsmeans trt / cl;
  ods output estimates=ESTIMATES lsmeans=lsmean; run;
```

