4.1 Overall Design

This Phase IV, low-interventional, multicenter, ambispective study will involve the evaluation of medical records of study participants treated with Cladribine Tablets or placebo (IMP) in the previously conducted parent studies. Long-term retrospective data will be collected through evaluation of medical charts/records, and additional prospective data will be

collected. No IMP will be administered as part of this study. An interim analysis is planned when data from approximately 100 patients are collected (see Section 9 for further details on analyses).

This study will collect data from study participants with MS who participated in the CLARITY/CLARITY-EXT clinical trial(s) and who received ≥ 1 course of IMP, or study participants with their FCDE who were randomized in the ORACLE MS study and received ≥ 1 course of IMP.

An overall Study Schema is depicted in Section 1.2. Additionally, details of the different timelines according to subject relapse status at the time of screening, and for participants completing the study remotely are presented in Section 1.2, and a detailed SoA is provided in Section 1.3.

Participants are invited to up to 3 clinic visits for this study. The first visit is the Screening Visit. The following screening activities may be administered by telephone if the patient is unable and/or not willing to attend clinic for the visit, depending on approval by Ethics Committees (ECs), Institutional Review Boards (IRBs), and/or local regulations: Informed consent (for patients participating in retrospective data collection only, local requirements for patient consent will be observed, which may include informed consent form [ICF] waiver), sociodemographic and clinical characteristics, medical and disease history, and study inclusion/exclusion determination.

Retrospective data for deceased or lost to follow-up patients will be collected in case an ICF waiver is granted, or proxy/caregiver/legal representative consent is obtained, depending on approval by ECs, IRBs, and/or local regulations.

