9.5 Handling of missing data/ Presentation of continuous and qualitative variables

It is anticipated that missing/not reported data will feature many of the endpoints, especially BVMT-R and SDMT (see section 14.3.3). No imputation will be done for these assessments.

In general, missing or partial dates will be imputed as follows:

- If year and month available but day is missing, impute day to 15
- If only year available, impute day and month to 15JUN
- If date is completely missing, then no imputation will be done, except for Concomitant Medication end dates: if end date is completely missing (day, month and year) and partial or complete start date then end date will be imputed to be the last study assessment date.

In addition, for concomitant medication dates:

- If imputed start date is after end date, then the start date will be set equal to end date.
- If imputed end date is before start date, then the end date will be set equal to start date.

For time to event analyses, if partial date does not determine whether event occurred before or after start date, then analysis date will be set equal to start date, subject will be censored and time to censoring = 1/365.25.

Continuous variables:

Continuous variables will be summarized using descriptive statistics, i.e.

- number of subjects (N),
- number of subjects with non-missing values,
- number of subjects with missing values
- mean and standard deviation,

- median, 25th Percentile - 75th Percentile (Q1-Q3),
- minimum, and maximum.

Qualitative variables:

Qualitative variables will be summarized by counts and percentages.

There are no plans for any formal statistical inference. This study will adhere to the Guidelines for Good Pharmacoepidemiology Practices (GPP). Data evaluation and interpretation will be based on point estimates and 95% corresponding confidence intervals (CI). Due to the exploratory nature of the study, an adjustment for multiple comparisons is not required.

Analyses will be performed using SAS® Software version 9.4 or higher.

10 Study Participants

The subsections in this section describe the specifications for reporting participant disposition and study discontinuations.

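### SAP 14.1 counts MS deaths as primary events but gives disease duration no end date for participants who died before Study Visit 1, so the adjusted models may lose those events or count duration past death

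*SAP*

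**What the plan says.** - **Endpoint.** SAP 14.1 lists the data sources for the primary endpoint and adds deaths: "Participants who died due to MS are included in this proportion also (reason of death is MS disease related". A chart EDSS of 8 or more at any time after the first dose also makes a participant an event.
- **Adjusted model.** For the pooled cohort the factors are parent study, "treatment group, and disease duration (at study visit 1) as continuous variable as factors for cohort A". For the others the model is fitted "with only disease duration (at study visit 1) as factors for cohort B, C and D". Disease duration is thus the one covariate common to all four cohort models.
- **Covariate.** SAP 14.1 computes it as (SV1 − date of MS diagnosis + 1)/365.25 and offers no alternative end date.
- **Code.** The printed PROC GENMOD step contains "model avalc = STUDY TRT DISEASE_DUR /dist=binomial link=logit lrci wald". Its only stated exclusion is an outcome coded U.
- **Missing dates.** SAP 9.5: "If date is completely missing, then no imputation will be done". The single exception is the end date of a concomitant medication.
- **Who can be enrolled.** Protocol 4.1: "Retrospective data for deceased or lost to follow-up patients will be collected in case an ICF waiver is granted", or with consent from a proxy, caregiver or legal representative. Participants already dead are therefore a planned part of the study.
- **What SV1 is.** Protocol 4.1 makes SV1 the occasion for abstracting the chart as well as for current assessments. The Schedule of Activities places most of the retrospective items in the SV1 column.

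**The concern.** Two rules in one section do not fit together. One deliberately brings in participants who died of MS. The other adjusts for a quantity whose end point is a study visit that someone who died beforehand could not attend. No text says what date to use for them.

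The adjusted proportion will be printed beside the crude one, with likelihood-based confidence intervals for the exposed and never-exposed groups. A reader will take a gap between the two as the result of adjustment. If part of the gap comes from records leaving the model, or from a covariate that keeps running after death, that reading is wrong. The participants concerned have the worst outcome on the scale.

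This is separate from the other weakness of the same covariate, that ORACLE participants who never converted to CDMS have no diagnosis date. Here the SV1 end of the interval is undefined, CLARITY participants are affected too, and the records at risk include confirmed events.

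**Working it through.** **1. Tracing one participant.** Take a participant who died of MS before enrolment and entered through a waiver or proxy.

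| Step | Rule | Result |
|---|---|---|
| Outcome | SAP 14.1, MS death | Event; kept by the U filter |
| SV1 date | Not defined for the deceased | Blank, or chart-abstraction date |
| If blank | SAP 9.5, no imputation | Duration missing; PROC GENMOD omits the record |
| If abstraction date | SAP 14.1 formula | Record kept; duration includes years after death |

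The multiple imputation in Protocol 9.4.1 is optional and is described for endpoint data. It sets no rule for this covariate.

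**2. The plan's own figure.** The only planning figures for this endpoint are the half-widths in Protocol 9.2. For n = 587 and 10%, a Wald interval with finite population correction gives

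1.96 × √(0.10 × 0.90/587) × √((1958 − 587)/1957) = 2.43% × 0.837 = 2.03%,

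as printed. Eleven of the twelve rows agree to two decimals. The twelfth (n = 1175, 10%) gives 1.09% against 1.08%, a rounding difference. This point disputes none of these figures; they serve only as a yardstick.

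**3. Blank SV1.** Let n be participants, e events and d MS deaths without SV1. If nothing else is lost, the model uses (e − d) events in (n − d) records. The documents give no value for d, so d is assumed at about 5%, 10%, 20% and 30% of events.

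| n = 587 | Crude | 5% | 10% | 20% | 30% |
|---|---|---|---|---|---|
| 29 events | 4.94% | 4.78% (d=1) | 4.45% (d=3) | 3.96% (d=6) | 3.46% (d=9) |
| 59 events | 10.05% | 9.59% (d=3) | 9.12% (d=6) | 8.17% (d=12) | 7.21% (d=18) |
| 88 events | 14.99% | 14.41% (d=4) | 13.67% (d=9) | 12.30% (d=18) | 11.05% (d=26) |

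For example, (59 − 12)/(587 − 12) = 47/575 = 8.17%. These are the raw proportions among the records the model would use.

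**4. If non-events are lost as well.** A blank SV1 could also remove participants scored as non-events, such as deaths from other causes. With 59 events, the proportion stays at 59/587 when (587 − 59)/59 = 8.9 non-events are lost per event lost. For d = 12 that is about 107. With fewer non-events lost the proportion falls; with more it rises.

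**5. Chart-abstraction date as SV1.** A logistic model with study, treatment and duration was fitted to one simulated data set (587 records, 60 events, 12 of them labelled MS deaths).

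- Duration blank for the 12: 575 records and 48 events used.
- Duration extended by 1 to 8 years after death for the 12: all 587 records and 60 events used, but the duration coefficient moved from 0.017 to 0.059 per year.

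All the extended records are events, so the added years look like risk from long disease. The values are illustrative; the direction follows from the construction.

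**The case against.** A reader might infer that every MS death disappears from the adjusted estimate in all four cohorts. The documents do not support that. Nowhere do they say that a deceased participant has no SV1 date. Protocol 4.1 collects chart data at SV1 for all patients, and the SAP anchors other quantities on SV1 without exception (age, ARR time on study, worst EDSS). A nominal SV1 date for chart-only participants is therefore a plausible reading, and under it nothing is deleted. A participant who dies of MS between SV1 and SV2 also has an SV1 date, and Protocol 4.1 gives remote participants an SV1 window. This part of the objection stands: the date is undefined, not shown to be absent. It does not rescue the formula, because the nominal date counts years after death as disease duration.

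A reader might also infer that the exposed versus never-exposed contrast is biased. That needs MS deaths to form a different share of events in the two groups. Suppose 47 events in 487 exposed and 12 in 100 never exposed, with 6 and 3 MS deaths. Deletion then moves the odds ratio from (47/440)/(12/88) = 0.78 to (41/440)/(9/88) = 0.91. With equal shares it stays at (41/440)/(10.47/88) = 0.78. The documents give no split, so no shift can be claimed.

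Finally, the crude percentage with its 95% CI is the main primary analysis, the regression is additional, and the study tests no hypothesis. That is correct and limits the weight of the point.

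**Conclusion.** The point holds as a gap in a stated derivation. SAP 14.1 counts MS deaths as events, ties the covariate of every cohort model to SV1 alone, and leaves deaths and losses before SV1 without a reference date. Either way of filling the gap damages the adjusted estimate, and sites could fill it differently.

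The size cannot be fixed from the documents. In the 587-participant, 10% scenario, 12 deaths without SV1 would shift the modelled proportion by 10.05 − 8.17 = 1.88 points, within the planned half-width of 2.03. Eighteen would shift it by 2.84 points, beyond it, but that assumes about 30% of all events are MS deaths. These shifts assume a blank SV1 and no non-event lost, so an unconditional statement that the adjusted proportion is too low is not supported. Under the chart-date reading the distortion lies in the duration effect and in whatever is adjusted by it.

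The SAP should be changed before the final analysis. The crude result does not depend on it.

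**What to change.** In SAP 14.1, define disease duration as (earliest of SV1, date of death and last recorded contact − date of MS diagnosis + 1)/365.25. Beside each adjusted estimate, print the records and events the model used next to the crude counts, so that any loss is visible.

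Disease duration at the first IMP dose looks simpler but should not be used unless the ORACLE diagnosis date is redefined too. SAP 14.1 dates diagnosis in ORACLE at CDMS conversion, which normally follows the first dose, so converters would have zero or negative durations. Non-converters have no diagnosis date under either definition and need their own rule.

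The cost is one derivation and two extra counts per table. No new assessment is needed. SAP 14.3.2 already treats MS death as an event in the time-to-ambulatory-device/wheelchair analysis, which requires a date of death, and last contact can be taken from the chart. The ARR denominator in 14.3.2 also runs to SV1, so the same end-date rule could serve there.
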